#### **6.3.4. Medical History and Concurrent medical conditions**

Medical history to be obtained will include determining whether the subject has any significant conditions or diseases relevant to the disease under study that stopped at or prior to signing of informed consent. Ongoing conditions are considered concurrent medical conditions.

Medication history information to be obtained includes any medication relevant to eligibility criteria and efficacy/safety evaluation stopped at or within 28 days prior to signing of informed consent.

Concurrent medical conditions are those significant ongoing conditions or diseases that are present at signing of informed consent. This includes clinically significant laboratory, electrocardiogram (ECG), or physical examination abnormalities noted at screening examination.

Medical history and concurrent medical conditions will be coded using the Medical Dictionary for Regulatory Activities (MedDRA), and will be tabulated for the number and percent of patients by decreasing frequency based on safety analysis set..

Individual medical history and concurrent medical conditions data will be listed.

### **6.3.5. Concomitant Medications**

Medication start and stop dates will be compared to the date of first dose of treatment to be classified as prior medications and concomitant medications.

Prior medications are those medications that start and stop prior to the date of first dose of study treatment. Concomitant medications is any drug given in addition to the study medication and defines as those medications that start before, on or after the first day of study treatment of the defined treatment period and continue into the treatment period and/or continue into 30 days after last dose or after the week 100 visit.

Concomitant therapy will be classified according to the World Health Organization Drug Dictionary (WHODRUG) and tabulated by WHO drug Anatomical Therapeutic Chemical (ATC) classification sorted by decreasing frequency and dose level based on safety analysis set.

Individual subject concomitant medication data will be listed.

## **6.4. Efficacy Analyses**

Efficacy analyses will be summarized using the FAS analysis set. Unless otherwise specified each summary of the efficacy variables will be presented for the primary time point (Week 96) as well as each planned visit. Only observed data will be summarized, and missing data will not be imputed. However, a visit called Final Visit will also be summarized; Final Value is defined as the last treatment phase value (ie. post-baseline and  $\leq$  Week 100).

A Pre-pubertal level will be any value less than ( $<$ ) the upper limit of normal for the local laboratory, which value may be dependent on sex and/or age. If laboratory values are converted to a common unit the normal ranges should also be converted, however all comparisons to the pre-pubertal level should be performed on the original unit.

The related variables for efficacy analyses will be presented for this study.

- Tanner staging
- peak LH and FSH
- basal estradiol (female) or testosterone level (male)
- predicted adult height
- the ratio of bone age to chronological age

The number and percentage of subjects who have regression or no progression in Tanner staging at Week 96 will be summarized, individual data will be listed.

The number and percentage of subjects with suppression of peak LH and FSH, i.e. simultaneously, after stimulation to pre-pubertal level at Week 96 (Visit 10) will be summarized, individual data will be listed. For each subject at each visit the peak value (i.e. largest value of the 0, 30, 60, 90 min samples) from the stimulation tests will be used,

The number and percentage of subjects with suppression of basal estradiol level in female subjects or testosterone level in male subjects to pre-pubertal level at Week 96 (Visit 10) will be summarized, individual data will be listed.

The number and percentage of subjects with improvement in predicted adult height at Week 96 (Visit 10) compared with Baseline will be summarized, individual data will be listed.

The number and percentage of subjects with a decrease in the ratio of bone age to chronological age at Week 96 (Visit 10) compared with Baseline will be summarized, individual data will be listed. Chronological age is determined using birthdate and date of the procedure to obtain age in days and then deviding by 365.25 to obtain age in years, not truncated to an integer.

For above binary data, 95% confidence intervals will be presented with exact (Clopper-Pearson) method.

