2.0 STUDY SUMMARY

Name of Sponsor(s): Takeda Development Center Asia, Pte. Ltd.	Compound: Leuprorelin			
Title of Protocol: An Open label, Multicenter Study to Assess the Safety and Efficacy of Leuprorelin in the Treatment of Central Precocious Puberty	IND No.: Not Applicable	EudraCT No.: Not Applicable		
Study Number: Leuprorelin-4001	Phase: 4			
Study Design: This is a phase 4, open label study to be conducted in China, to assess long-term safety and efficacy of Leuprorelin in the treatment of central precocious puberty (CPP). Approximately 300 subjects will be enrolled. The treatment duration is 96 weeks. The study will consist of 3 periods including a 4-week Screening Period, a 96-week Treatment Period and a 4-week Safety Follow-up Period. After the end of the study, subjects will participate in an observational follow-up, in which subjects who remain on treatment will be observed at least every 24 weeks. All subjects will be followed up annually after the last dose until stable puberty is reached.				
Primary Objective: To evaluate the safety of leuprorelin in subjects with CPP				
Secondary Objective: To evaluate the efficacy of leuprorelin in subjects with CPP				
Subject Population: Subjects with appearance of secondary sexual characteristics before 8.0 years in girls and before 9.0 years in boys, with confirmed diagnosis of CPP.				
Number of Subjects: Estimated total: 300	Number of Sites: Approximately 10-15 sites in China			
Dose Level(s): CPP subjects with body weight \geq 20 kg will receive the recommended dose of leuprorelin 3.75 mg subcutaneous administration (SC) every 4 weeks. Subjects with body weight $<$ 20 kg will receive recommended dose of 1.88 mg SC every 4 weeks. It is not recommended to exceed 180 μ g/kg.	Route of Administration: Subcutaneous			
Duration of Treatment: 96 weeks	Period of Evaluation: 4 weeks Screening Period 96 weeks Treatment Period 4 weeks Safety Follow-up Period Observational Follow-up until stable puberty is reached			
Main Criteria for Inclusion: 
 ● In the opinion of the investigator, the subject and/or parent(s) or legal guardian are capable of understanding and complying with protocol requirements. 				

CONFIDENTIAL

Leuprorelin

Study No. Leuprorelin-4001

Protocol Amendment #1

Page 11 of 73

16 Dec 2015

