4.0 INTRODUCTION

4.1 Background

Precocious puberty refers to appearance of secondary sexual characteristics in boys before 9 years and girls before 8 years. Children with central precocious puberty (CPP) have premature secretion and release of gonadotropin releasing hormone (GnRH) in the hypothalamus, activating secretion of gonadotropin by the pituitary gland, promoting development of the gonads and secretion of sex hormones, resulting in development of internal and external genital organs and appearance of secondary sexual characteristics [1].

The early onset of secondary characteristics can be psychologically and emotionally difficult for a young child. The young child does not understand the changes in his/her body and the emotional changes he or she is experiencing. The large size of the child due to the puberty growth spurt often causes further stress because of the greater expectations of parents and teachers because he/she seems older. Although intelligence and social skills do not advance with the child's size, he/she may be pushed ahead in school or in social situations because of this. The child is no longer like his/her peers, but rather a child's mind in a small adult body [2]. In China, the incidence of CPP is increasing. Epidemiology studies showed that the incidence of CPP in children aged 6-9 years in Zhejiang province is about 0.38% [3] and 1% in Shanghai [4]. The ratio of girls to boys is about 4-5 to 1 [4].

CPP is controlled by the hypothalamic-pituitary-gonadal axis, the same mechanism that controls normal puberty. If the reproductive hormonal cycle can be interrupted, the child can be returned to a prepubertal state. Halting this process means suppressing the pituitary so that gonadotropins will decrease to prepubertal levels. Due to the negative feedback mechanism, the gonads will follow suit, then, suppression of gonadotropins and sex steroids will trigger decreases in growth and bone maturation and will also halt the development of secondary sexual characteristics. GnRH analogs (GnRHa) have been the standard of care for CPP. Continuous exposure to GnRHa desensitizes pituitary gonadotroph receptors and suppresses luteinizing hormone (LH) and follicle-stimulating hormone (FSH) secretion [1].

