9.1.8 Procedures for Clinical Laboratory Samples

All samples will be collected in accordance with acceptable laboratory procedures. The maximum volume of blood at any single visit is approximately 40 mL, and the approximate total volume of blood for the study is 200 mL.

Table 9.a Clinical Laboratory Tests

Hematology	Clinical Chemistry	Urinalysis
RBC	ALT	pH
WBC	Albumin	Specific gravity
Hemoglobin	Alkaline phosphatase	Protein
Hematocrit	AST	Glucose
Platelets	Total bilirubin	Blood
	Total protein	Nitrite
	Creatinine	
	Blood urea nitrogen	Microscopic Analysis (only if positive dipstick results):
	Creatine kinase	RBC/high power field
	GGT	WBC/high power field
	Potassium	Epithelial cells, casts etc
	Sodium	
	Glucose	
	Chloride	
	Bicarbonate	
	Calcium	
	Magnesium	
Other:		
GnRH stimulation test		
LH and FSH		
Estradiol or testosterone		
Serum bone metabolism biomarkers- phosphorus, 25-hydroxy vitamin D, osteocalcin, crosslaps		
Other Screening/Safety		Urine
AFP, CEA, β -HCG		Urine pregnancy test *

AFP= alpha-fetoprotein, β -HCG= beta human chorionic gonadotropin, CEA=carcino-embryonic antigen, GGT= glutamyl transferase, RBC=red blood cells, WBC=white blood cells.

*The female subject who, at the discretion of the investigator, is deemed to be of child bearing potential must provide negative urine pregnancy test at Day -1 or Day 1 prior to drug administration.

The local laboratory will perform laboratory tests for hematology, serum chemistries, urinalysis, estradiol, testosterone, bone metabolism markers, LH, FSH, AFP, CEA, and β -HCG. The results of laboratory tests will be returned to the investigator, who is responsible for reviewing and filing these results.

If subjects experience ALT or AST $>3 \times$ ULN, follow-up laboratory tests (at a minimum, serum alkaline phosphatase, ALT, AST, total bilirubin, GGT, and INR) should be performed within a maximum of 7 days and preferably within 48-72 hours after the abnormality was noted.

(Please refer to Section 0 for discontinuation criteria, and Section 10.2.3 for the appropriate guidance on Reporting of Abnormal Liver Function Tests in relation to ALT or AST $>3 \times$ ULN in conjunction with total bilirubin $>2 \times$ ULN.)

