#### **2.2.3. Additional Endpoints**

- Percentage of subjects with suppression of peak luteinizing hormone (LH) and follicle-stimulating hormone (FSH) to pre-pubertal levels in stimulation test at Week 96.
- Percentage of subjects with suppression of basal estradiol level in female subjects or testosterone level in male subjects to pre-pubertal level at Week 96.
- Percentage of subjects with improvement in predicted adult height at Week 96 compared with Baseline.
- Percentage of subjects with a decrease in the ratio of bone age (BA) to chronological age at Week 96 compared with Baseline.

- Change in laboratory values including changes in chemistry, hematology and bone metabolism biomarkers.
- Change in body mass index (BMI).
- Change in bone mineral density.
- Incidence of polycystic ovarian syndrome in female subjects.

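### The limit that defines a pre-pubertal hormone level may depend on age and is not fixed within a child, so some children who are not suppressed at Week 96 could be counted as suppressed

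*SAP*

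**What the plan says.** The endpoint in SAP 2.2.3 is the "Percentage of subjects with suppression of basal estradiol level in female subjects or testosterone level in male subjects to pre-pubertal level at Week 96". A companion endpoint asks the same of peak LH and FSH in the stimulation test. Protocol 5.2.3 and 13.1.3 list both and do not define a pre-pubertal level.

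The definition comes in SAP 6.4. A pre-pubertal level is any value less than "the upper limit of normal for the local laboratory, which value may be dependent on sex and/or age". The only other instruction about applying the limit concerns units: "all comparisons to the pre-pubertal level should be performed on the original unit". Nothing in the section names a Tanner I or other pre-pubertal reference group. Nothing says whether age is taken at Baseline or at the visit, or holds the limit constant within a child.

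The hormone rule looks at the Week 96 value alone. Elsewhere in SAP 6.4 the plan does refer back to Baseline, for example "improvement in predicted adult height at Week 96 (Visit 10) compared with Baseline".

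There is no central range. Protocol 9.1.8 states: "The local laboratory will perform laboratory tests for hematology, serum chemistries, urinalysis, estradiol, testosterone". The same sentence includes LH and FSH. The Study Summary gives "Approximately 10-15 sites in China".

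**The concern.** A pre-pubertal level is meant to describe a state to which treatment returns the child. Protocol 4.1 puts the aim for gonadotropins this way: "Halting this process means suppressing the pituitary so that gonadotropins will decrease to prepubertal levels". An upper limit of normal for a child's age is a different thing. It describes what is usual at that age, and at ages when puberty is normally under way it may include pubertal values.

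If the limit moves up as the child ages, a value that has not fallen can pass below it. The study has one arm, so no comparison group shares the shift, and the reported percentage would credit it to treatment. The children at risk of being miscounted are those with incomplete suppression, which Protocol 4.2 names as a reason for concern about low dosing. The Week 96 results go to the CFDA (SAP 6.7).

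**Working it through.** **Plan's own figure.** There is none to reproduce. Neither document states an expected suppression rate, and the sample size of about 300 is not derived from a formula.

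**1. How much a child ages.** SAP Table 6.a places Week 96 at Day 672 with a window of ±14 days.
- 672 / 365.25 = 1.84 years
- 658 / 365.25 = 1.80 years and 686 / 365.25 = 1.88 years at the window's ends

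Inclusion criterion 3 caps age at onset (girls 8.0 years, boys 9.0 years), not age at enrolment. A girl enrolled at 8.0 is 8.0 + 1.84 = 9.84 at Week 96, and a boy enrolled at 9.0 is 10.84. Children enrolled later are older.

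**2. Chance of entering a new age band.** Band widths are assumed, because the documents give none. If ages are uniform within bands of width w years, the chance of crossing at least one edge is min(1, 1.84 / w).

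| Band width (years) | 1 | 2 | 3 | 4 | 5 |
|---|---|---|---|---|---|
| Chance of crossing | 100% | 92% | 61% | 46% | 37% |

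Crossing an edge matters only if the limit is higher on the other side.

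**3. What the rule does to one child.** Assume, in arbitrary units, a limit of 10 at the Baseline age and 15 at the Week 96 age.

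| Baseline value | Week 96 value | Limit read at visit age | Limit fixed at Baseline |
|---|---|---|---|
| 12 | 12 | suppressed | not suppressed |
| 12 | 14 | suppressed | not suppressed |
| 8 | 8 | suppressed | suppressed |
| 8 | 9.5 | suppressed | suppressed |

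The first two rows are the problem described here. The last two are a separate matter: a child already below the limit at Baseline counts as suppressed under either reading, and fixing the limit does not change that.

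**4. Effect on the reported percentage.** Let p be the true proportion suppressed and m the share of the non-suppressed children who fall under the higher limit. Then reported rate = p + (1 − p)m, and the excess is (1 − p)m. Both p and m are assumed. The intervals are exact (Clopper-Pearson) 95%, the method named in SAP 6.4. They use n = 300, rounded to whole children, as if every child had a Week 96 value.

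| True p | m = 10% | m = 25% | m = 50% |
|---|---|---|---|
| 70% | 73.0% (67.6-77.9) | 77.3% (72.2-81.9) | 85.0% (80.4-88.8) |
| 80% | 82.0% (77.2-86.2) | 85.0% (80.4-88.8) | 90.0% (86.0-93.2) |
| 90% | 91.0% (87.2-94.0) | 92.7% (89.1-95.3) | 95.0% (91.9-97.2) |

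The smallest excess is 0.10 × 0.10 = 1 point and the largest is 0.30 × 0.50 = 15 points. In five of the nine cases the interval excludes the true rate: p = 70% or 80% with m = 25% or 50%, and p = 90% with m = 50%. If limits do not change between the two ages, m = 0 and there is no excess.

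**The case against.** **The SAP does not say that the limit is read on the day of the test.** A reader might infer that it does. The nearest convention in SAP 6.4, for chronological age in the bone-age ratio, uses the date of the procedure, and a laboratory range normally accompanies the result it judges. But that convention is not stated for hormones, and Baseline age remains an open reading under which the limit would not rise with age. This stands. What remains is that the text allows both readings, and they can give different percentages.

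**No ranges are given.** Whether any limit rises over these ages, and by how much, cannot be learned from the documents. A reader might also infer that older children gain most; that would depend on where each laboratory's band edges fall, which is not shown.

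**A much larger effect is tempting.** Suppose every child's limit rises k-fold, the log ratio of hormone to Baseline limit is centred on 0, and no child's hormone changes. The share newly below the limit is then Φ(ln k / SD) − 0.5. For log SDs from 1.0 to 0.5 this is 16-29% at k = 1.5 and 26-42% at k = 2. The documents do not support using this as the bias. Protocol 4.1 expects sex steroids to fall to prepubertal levels, and only children not suppressed at Week 96 can be miscounted.

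**The endpoint is not a transition.** A reader might infer that it counts children who move from above the limit to below it. It classifies the Week 96 value only.

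**Some of this would be visible.** SAP 6.4 also summarises each planned visit and lists individual data, and estradiol or testosterone is measured from Visit 2 to Visit 11. Week 12, with little ageing, can be set beside Week 96. This helps, but the SAP does not call for listing the limit applied, so a reader could not separate a change in hormone from a change in limit.

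**Conclusion.** The point holds in conditional form. SAP 6.4 permits a limit that depends on age, does not anchor it to a pre-pubertal group and does not fix the age at which it is read. This is more than missing detail, because under one natural reading the rule can misclassify a child. Where the limit rises with age, the error runs towards success. It applies to estradiol/testosterone and to peak LH and FSH.

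The size cannot be determined from the documents. The range of about 1 to 15 percentage points rests on assumed true suppression of 70-90% and an assumed 10-50% of non-suppressed children being reclassified. It is zero in laboratories whose limits do not change over the ages concerned, and zero throughout if the limit is read at Baseline age.

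Priority is modest. These are additional endpoints, below the primary (TEAE) and secondary (Tanner staging) endpoints, in a study with no hypothesis test.

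**What to change.** In SAP 6.4:

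- Use one fixed, sex-specific pre-pubertal (Tanner I) limit per laboratory and assay for each hormone, at Baseline and at all visits.
- Where a laboratory has no such range, freeze the limit at the child's Baseline age and flag those children, because that limit may not be strictly pre-pubertal.
- List the limit applied to each value.
- As a sensitivity analysis, report how many children change class when the limit for the visit age is used.

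The cost is SAP wording and one reference value per laboratory and hormone, by sex where needed. Estradiol is needed for girls, testosterone for boys, and LH and FSH for both, which makes 1 + 1 + 2 + 2 = 6 limits per laboratory. With one laboratory and one assay per site, that is 60 values for 10 sites and 90 for 15. Protocol 9.1.8 already has the investigator keep the laboratory's reference ranges, and no new data from children are needed. The downside is that the reported suppression rate may be lower.

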7.1 Inclusion Criteria

Subject eligibility is determined according to the following criteria prior to entry into the study:

1. In the opinion of the investigator, the subject and/or parent(s) or legal guardian are capable of understanding and complying with protocol requirements.
2. The subject or the subject's parent(s) or legally acceptable representative signs and dates a written, informed consent form and any required privacy authorization prior to the initiation of any study procedures.
3. The subject has age of onset of appearance of secondary sexual characteristic earlier than age 8.0 years in girls or earlier than 9.0 years in boys and the symptom is persistent, and has confirmed diagnosis of CPP.
4. The subject has basal LH level >5.0 IU/L or peak LH >5.0 IU/L in stimulation test OR peak LH >3.3 IU/L with LH/follicle-stimulating hormone (FSH) >0.6 in stimulating test. The subject has evidence of gonadal development evaluated by ultrasonography: multiple ovarian follicles ≥ 4 mm in any ovary or uterine enlargement in females or testicular volume ≥ 4 mL in males.
5. The subject has advanced BA ≥ 1 year and BA is ≤ 11.5 years in females or ≤ 12.5 years in males OR predicted adult height <150 cm in females or < 160 cm in males OR SDS $<-2SD$ OR rapid growth defined as growth of BA /growth of chronologic age >1 . BA is determined by Greulich and Pyle standards or Tanner-Whitehouse 3 (TW3) standards at screening.
6. The subject has anticipated treatment duration of at least 2 year in investigator's judgment.
7. A male subject who is nonsterilized* and sexually active with a female partner of childbearing potential* agrees to use adequate contraception* from signing of informed consent throughout the duration of the study and for 90 days after last dose.
8. A female subject of childbearing potential* who is sexually active with a nonsterilized* male partner agrees to use routinely adequate contraception* from signing of informed consent throughout the duration of the study and for 90 days after last dose of study medication.

*Definitions and acceptable methods of contraception are defined in Section 9.1.9 Contraception and Pregnancy Avoidance Procedure and reporting responsibilities are defined in Section 9.1.10 Pregnancy.

9. The female subject who, at the discretion of the investigator, is deemed to be of child bearing potential must provide negative urine pregnancy test at test Day -1 or Day 1 prior to receiving

CONFIDENTIAL

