(j) Bone mineral density will be evaluated by dual energy x-ray bone densitometry at selected sites, which can done at any time prior to the first dose after the Screening. Estradiol or Testosterone and Serum bone metabolism biomark also can be done at any time prior to first dose as part of screening visit. (k) Serum bone metabolism biomarker included phosphorus, 25-hydroxy vitamin D, osteocalcin, crosslaps. These 4 tests can be performed as per what is available at the given Site. These tests can done at any time prior to the first dose after the Screening.

(l) Subcutaneous injection Leuprorelin every 4 weeks. For the dosing visits between Visits 2-3, between Visits 3-4, between Visits 4-5, between visits 5-6, between visits 6-7, between 7-8, between 8-9, between visits 9-10: these visit window is +/- 2 days; in addition, the between gap between dosing cannot be less than 3 weeks (21 days).

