#### 5. ANALYSIS SETS

- Safety Analysis Set (SS): The SS consists of all subjects who are enrolled and received at least 1 dose of study drug.
- Full Analysis Set (FAS): The FAS consists of all subjects who are enrolled and received at least 1 dose of study drug.

- Per Protocol Analysis Set (PPS): The PPS consists of all subjects who are in the FAS and have none of the following major protocol violations:

- Subject doesn't complete the Week 96 visit;
- Subject has less than 90% treatment compliance;
- Subject fails to meet inclusion criteria No.s: 3, 4 and 6;
- Subject meets exclusion criteria No.s: 1, 2, 4, 5, 6, and 8.

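### The Week 96 estradiol/testosterone 'suppression' percentage has no Baseline condition, so it combines raised values that fell with values already below the limit

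*SAP*

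**What the plan says.** The sex-steroid result is one of the additional endpoints (Protocol 5.2.3, SAP 2.2.3). SAP 6.4 gives a count and a percentage for "subjects with suppression of basal estradiol level in female subjects or testosterone level in male subjects to pre-pubertal level at Week 96", with exact Clopper-Pearson 95% limits.

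- **Cut-off (SAP 6.4):** "A Pre-pubertal level will be any value less than ( $<$ ) the upper limit of normal for the local laboratory". The limit may vary with sex and age.
- **Analysis set:** "Efficacy analyses will be summarized using the FAS analysis set" (SAP 6.4), and "The FAS consists of all subjects who are enrolled and received at least 1 dose of study drug" (SAP 5). Missing values are not imputed.
- **Contrast:** for predicted adult height and the bone-age ratio, SAP 6.4 writes in a comparison with Baseline. For the sex steroids it does not.
- **Entry (Protocol 7.1):** criterion 4 is hormonal but concerns LH: "The subject has basal LH level >5.0 IU/L or peak LH >5.0 IU/L in stimulation test OR peak LH >3.3 IU/L", the last route also needing an LH/FSH ratio above 0.6. It adds that "The subject has evidence of gonadal development evaluated by ultrasonography". Criterion 5 concerns bone age, predicted height, SDS or growth. No inclusion or exclusion criterion refers to estradiol or testosterone.
- **Baseline value:** it is drawn at Visit 2, or earlier: "Estradiol or Testosterone and Serum bone metabolism biomark also can be done at any time prior to first dose as part of screening visit" (Protocol Appendix A, footnote j). SAP 6.3.3 summarises it as a baseline characteristic. No responder rule uses it.

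**The concern.** A child can enter on a stimulated LH peak with basal estradiol or testosterone already below the limit. If the value is still below it at Week 96, the working rule counts that child as suppressed, although no raised value was brought down. Protocol 4.1 describes the drug's action as lowering sex steroids to prepubertal levels, and a reader of the report will take 'suppression' in that sense.

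The study has one arm, so no control group separates starting status from change on treatment. The Week 96 results go to the CFDA as efficacy data (Protocol 6.1 and 13.2, SAP 6.7). If many children start below the limit, the percentage and its interval could be read as a suppression rate that they do not estimate.

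**Working it through.** **Figure to reproduce.** There is none. The documents give no expected suppression rate, no share low at Baseline and no precision target; the sample size of about 300 is stated without inputs.

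**Inputs, all assumed except N**
- N = 300 (SAP 4), taken as all observed at Week 96. Observed-case reporting would make the real denominators smaller.
- p = share below the limit at Baseline: 20, 40, 60%.
- q = share of Baseline-raised children below the limit at Week 96: 70, 90%.
- r = share of Baseline-low children below the limit at Week 96: 100%, with 95% as a check.

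**Formulae**
- Percentage under the SAP rule = p·r + (1 − p)·q.
- Rate in Baseline-raised children = q, on 300(1 − p) children.
- Difference = p·r + (1 − p)·q − q = p(r − q).

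**Results with r = 100% (exact 95% limits)**

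| q | p | SAP rule, all subjects | Baseline-raised only | Difference |
|---|---|---|---|---|
| 90% | 20% | 276/300 = 92.0% (88.3 to 94.8) | 216/240 = 90.0% (85.5 to 93.5) | +2 |
| 90% | 40% | 282/300 = 94.0% (90.7 to 96.4) | 162/180 = 90.0% (84.7 to 94.0) | +4 |
| 90% | 60% | 288/300 = 96.0% (93.1 to 97.9) | 108/120 = 90.0% (83.2 to 94.7) | +6 |
| 70% | 20% | 228/300 = 76.0% (70.8 to 80.7) | 168/240 = 70.0% (63.8 to 75.7) | +6 |
| 70% | 40% | 246/300 = 82.0% (77.2 to 86.2) | 126/180 = 70.0% (62.7 to 76.6) | +12 |
| 70% | 60% | 264/300 = 88.0% (83.8 to 91.5) | 84/120 = 70.0% (61.0 to 78.0) | +18 |

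**Sensitivity to r.** At r = 95% and q = 70%, p(r − q) is 0.2 × 25 = 5, 0.4 × 25 = 10 and 0.6 × 25 = 15 points. At r = 95% and q = 90% it is 1, 2 and 3 points. If r = q it is zero. If r < q it is negative: p = 40%, r = 85%, q = 90% gives 0.4 × (−5) = −2 points.

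**Why the rule needs stating.** Suppose instead that 'suppression' requires a raised Baseline value. The SAP does not say whether Baseline-low children then leave the denominator or count as failures. At p = 40%, q = 70%, r = 100%, the same data give 246/300 = 82% under the literal rule, 126/180 = 70% if they leave, and 126/300 = 42% if they count as failures.

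**The case against.** **Suppression may be meant as a fall from a higher value.** The word allows that reading, so the intention cannot be taken as certain. But the SAP's only working definition looks at the current value, and the other reading leaves the denominator undefined. Either way the text needs a rule.

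**Staying low can be a drug effect.** This stands. Entrants have confirmed CPP, a qualifying LH and gonadal development. Protocol 4.1 describes an activated axis that drives sex-hormone secretion, and the secondary endpoint itself counts absence of Tanner progression as success. A reader might infer that Baseline-low children are simply artefact, or that the exact interval surrounds a wrong quantity. The documents do not support that: nothing in them shows such children would have stayed low untreated, and the interval is correct for the proportion below the limit at Week 96.

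**The true rate may be high.** Protocol 4.1 says sex steroids usually reach prepubertal levels within 2 to 4 weeks of starting treatment. That points towards the q = 90% rows, where the difference is 2 to 6 points. It is background rather than an estimate for this cohort, so both rows are shown.

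**Planned output already helps.** In part. SAP 6.4 summarises each planned visit and lists individual data, so the share low at Baseline may be visible. Separate percentages by visit do not show which children changed status, and listings give no prespecified estimate or interval.

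**Restricting the denominator has its own bias.** This stands too. Selecting children on one high Baseline value invites regression to the mean, so some would fall below the limit on re-measurement without any treatment effect. The restricted rate should therefore be added alongside the all-subject figure, not replace it.

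**Conclusion.** The point holds as one of definition and labelling. Under the SAP's working rule, the Week 96 percentage is the proportion below the limit, and it exceeds the suppression rate in Baseline-raised children by p(r − q). With r = 100% and p from 20% to 60%, that is 2 to 6 points at q = 90% and 6 to 18 points at q = 70%. All three quantities are assumptions, and the actual size cannot be found from the documents.

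It would be tempting to conclude that the error always favours the drug. It does so only when r exceeds q, which is plausible but not established.

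The consequence is limited. This is an additional endpoint, the study is not powered for any hypothesis test, no decision rule uses the result, and the values needed are already collected. Clarification is worthwhile and cheap; the defect does not threaten the primary or secondary endpoint.

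**What to change.** In SAP 6.4:

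1. Keep the all-FAS percentage and its exact interval, but label it 'below the limit at Week 96' and not 'suppression'.
2. Add a Baseline-by-Week-96 shift table (below the limit against at or above it), by sex and overall, with missing values shown.
3. Add the percentage with exact 95% interval among children at or above the limit at Baseline and observed at Week 96.
4. For items 2 and 3, classify both time points against one prespecified limit per child, for example the sex and age limit that applied at Baseline. The SAP's cut-off is "the upper limit of normal for the local laboratory, which value may be dependent on sex and/or age", and the child ages nearly two years, so a change of age band alone could otherwise change status. If the all-FAS figure keeps the limit current at Week 96, footnote that the two can differ for individual children.

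**Cost.** SAP wording, one table and one extra percentage, with no new data collection. The subset is smaller and its interval wider, most of all in boys. At the 4 to 5 girls per boy cited in Protocol 4.1, 300 children would include about 300/5 = 60 to 300/6 = 50 boys; at p = 40%, only 36 to 30 would be in the subset. The report should also note regression to the mean from selecting on a single Baseline value.
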